6.1.3 Unblinding

If a subject becomes pregnant or seriously ill during the study, the blind should be broken only if knowledge of the study medication dose administered will affect treatment options available

to the subject. Before breaking the blind, the investigator should contact the sponsor’s Medical Monitor/designee for discussion on whether unblinding of the subject is warranted. If warranted, the principal investigator or designee will place an unblinding call to the IWRS to receive treatment assignment information. In the case of an extreme emergency and if the Medical Monitor is immediately unreachable, the investigator should break the blind through the IWRS. Please see the Investigator Site File for further details.

In the event prior authorization from the sponsor’s Medical Monitor is not possible, the sponsor’s Medical Monitor must be notified by telephone immediately, but no later than 24 hours following the unblinding of any subject for any reason. A record should be kept of when the blind was broken, who broke it, and why.

6.1.4 Dose Interruption of Individual Subjects

Teduglutide administration for an individual subject may need to be stopped if the subject has an adverse event of special interest (see risks in table below) that is severe in intensity [Grade 3 or higher as defined by the National Cancer Institute’s Common Terminology Criteria for Adverse Events (CTCAE)]. This may occur if an event is attributable to study drug or a subject experiences an unexplained CTCAE Grade 3 or higher that is not reasonably related to the underlying disease process. The determination of length of the discontinuation, temporary or permanent, depends on the clinical situation.

Investigators and the DSMB should be guided by the descriptions of Grade 3 and 4 events below, as they relate to identified risks associated with the administration of teduglutide.

Identified Risk	Grade 3 Description	Grade 4 Description
Gastrointestinal Disorders		
Colorectal polyps	Severe or medically significant but not immediately life threatening; hospitalization or prolongation of existing hospitalization indicated; disabling; limiting self-care activities of daily living	Life-threatening consequences; urgent intervention indicated
Intestinal Obstruction	Hospitalization indicated; elective operative intervention indicated; limiting self-care activities of daily living; disabling	Life-threatening consequences; urgent operative intervention indicated
Gallbladder and Bile Duct Disease		
Cholecystitis	Severe symptoms; radiologic, endoscopic or elective operative intervention indicated	Life-threatening consequences; urgent operative intervention indicated
Gallbladder perforation	Not Applicable	Life-threatening consequences; urgent intervention indicated
Gallbladder obstruction	Symptomatic and severely altered gastrointestinal function; tube feeding, total parenteral nutrition or hospitalization indicated; nonemergent operative intervention indicated	Life-threatening consequences; urgent operative intervention indicated

Identified Risk	Grade 3 Description	Grade 4 Description
Gallbladder infection	Intravenous antibiotic, antifungal, or antiviral intervention indicated; radiologic, endoscopic, or operative intervention indicated	Life-threatening consequences; urgent intervention indicated
Alkaline Phosphatase increased	> 5.0 to 20.0 x Upper limit of normal	> 20.0 x Upper limit of normal
Blood bilirubin increased	> 3.0 to 10.0 x Upper limit of normal	> 10.0 x Upper limit of normal
Bile duct stenosis	Severely altered gastrointestinal function; radiologic, endoscopic or elective operative intervention indicated	Life-threatening consequences; urgent operative intervention indicated
Pancreatic Disease		
Pancreatitis	Severe pain; vomiting; medical intervention indicated (eg, analgesia, nutritional support)	Life-threatening consequences; urgent intervention indicated
Pancreatic duct stenosis	Severely altered gastrointestinal function; tube feeding or hospitalization indicated; elective operative intervention indicated	Life-threatening consequences; urgent operative intervention indicated
Pancreas infection	Intravenous antibiotic, antifungal, or antiviral intervention indicated; radiologic or operative intervention indicated	Life-threatening consequences; urgent intervention indicated
Serum amylase increased ^a	> 2.0 to 5.0 x Upper limit of normal	> 5.0 x Upper limit of normal
Lipase increased ^a	> 2.0 to 5.0 x Upper limit of normal	> 5.0 x Upper limit of normal
Cardiovascular Disease		
Heart failure	Severe with symptoms at rest or with minimal activity or exertion; intervention indicated	Life-threatening consequences; urgent intervention indicated (eg, continuous intravenous therapy or mechanical hemodynamic support)
^a In the setting of clinically acute and symptomatic pancreatitis Source: Common Terminology Criteria for Adverse Events, version 4.03, 14 June 2010		

6.1.5 Early Termination of the Clinical Study

The DSMB may recommend stopping the study if:

- ≥ 2 subjects being administered study drug develop the same CTCAE Grade 3 or
- 1 subject develops a CTCAE Grade 4 adverse event which is attributable to study drug or is not reasonably related to the underlying disease process

6.1.6 Laboratory Evaluations

The following laboratory parameters will be examined according to the Schedules of Evaluations and Procedures as outlined in [Table 6-1](#) and [Table 6-2](#) ([Table 6-3](#) and [Table 6-4](#) for the standard of care group). While not all abnormal laboratory results would be considered

clinically significant as determined by the investigator (ie, those that are associated with the disease state and were present at baseline), those that are determined to be a clinically significant change (ie, worsening) from baseline or known medical history will be considered adverse events. All such abnormal laboratory values that are considered AEs must be recorded on the appropriate eCRF. A result outside of the normal range may be repeated for confirmation. Any laboratory test result that meets the criteria for an SAE (Section 6.1.2) must also be recorded in an SAE report so that the sponsor/designee can collect additional information about that abnormality, including information regarding relationship to investigational product or other causes, any action taken, and outcome.

Laboratory collections that are required at intervals that do not coincide with clinic visits (ie, for safety lab assessments done following PN/IV adjustments) may be obtained by a Home Health Agency at subjects' homes.

6.1.6.1 Safety Laboratory Tests and Procedures

Hematology

Hemoglobin	Red blood cell (RBC) count
Hematocrit	White blood cell (WBC) count with differential
Platelets	RBC morphology, if needed

Serum Chemistry

Albumin	C-reactive protein
Alkaline phosphatase	Estimated Glomerular Filtration Rate [eGFR] (Schwartz formula)
ALT	Glucose
Amylase	Gamma glutamyl transferase
AST	Lipase
Bicarbonate	Magnesium
Bilirubin (total and indirect)	Phosphorus
Blood urea nitrogen	Potassium
Calcium (total)	Sodium
Chloride	Triglycerides
Cholesterol	Uric acid
Citrulline (plasma)	
Creatinine	

Urinalysis

Blood	pH and osmolality
Glucose	Protein
Leucocytes	Sodium
Microscopic analysis	Pregnancy tests (females of child-bearing potential) – for active treatment group only
Specific gravity	

Procedures

Upper GI series with small bowel follow through

Abdominal ultrasound

Colonoscopy/sigmoidoscopy (subjects 12 years and older or if fecal occult blood testing result is positive regardless of age without a documented or known etiology to explain the fecal positive results, ie, fissures, etc.).

Fecal occult blood testing

6.1.6.2 Plasma Citrulline

Plasma citrulline will be measured as an assessment of enterocyte mass, according to the Schedules of Evaluations and Procedures (Table 6-1 and Table 6-2). Citrulline should be collected 2 to 4 hours postprandially, whenever possible. Blood samples for citrulline may be drawn from a central line or from peripheral access. The samples will be processed according to instructions in the Laboratory Manual and will be collected from subjects from both active treatment and standard of care groups who participate in this study.

6.1.6.3 Antibodies to Teduglutide

Blood samples will be drawn only from the active treatment groups for the analysis of positive/specific antibodies to teduglutide according to the Schedules of Evaluations and Procedures (Table 6-1 and Table 6-2). Blood samples for antibodies may be drawn from a central line or from peripheral access.

6.1.7 Physical Examinations

Complete and comprehensive physical examinations will be performed by a medically qualified person during the study to assess the subject's physical status, according to the Schedules of Evaluations and Procedures (Table 6-1 and Table 6-2) (Table 6-3 and Table 6-4 for the standard of care group).

Any significant finding at baseline, such as hepatomegaly, should be included in the subject's medical history eCRF. Any clinically significant changes from baseline (in the opinion of the investigator) noted during the physical examinations, whether or not these procedures are required by the protocol, should be recorded on the appropriate AE page of the eCRF. This will assist the sponsor/designee in collecting additional information about that abnormality, including information regarding relationship to investigational product or other causes, any action taken, and outcome.

6.1.8 Vital Signs and Body Weight

Vital signs will be measured according to the Schedules of Evaluations and Procedures (Table 6-1 and Table 6-2) (Table 6-3 and Table 6-4 for the standard of care group). Measurements will include systolic and diastolic blood pressure (mmHg), pulse (beats per minute), and body temperature (°C/°F). Body weight (kg) will also be recorded on the eCRF; subjects should be weighed on the same scale at each study visit. Height (or length [cm]) and head circumference (in cm for subjects ≤ 36 months of age) will be measured at selected visits.

A height Z-score, weight Z-score, BMI, and BMI Z-score will be calculated by the sponsor using the site-provided height and weight data collected at each site visit.

Any clinically significant changes (ie, worsening) in the opinion of the investigator noted in vital signs assessments (ie, those that are associated with the disease state and were present at baseline), should be recorded on the appropriate AE page of the eCRF. This will assist the

sponsor/designee in collecting additional information about that abnormality, including information regarding relationship to investigational product or other causes, any action taken, and outcome.

6.1.9 Electrocardiograms

Twelve-lead electrocardiograms will be performed according to the Schedules of Evaluations and Procedures ([Table 6-1](#) and [Table 6-2](#); [Table 6-3](#) and [Table 6-4](#) for the standard of care group). The ECG tracing will be read by a local experienced physician. Results (normal, abnormal not clinically significant, and abnormal clinically significant with description of the finding) will be recorded on the eCRFs.

Any clinically significant changes from baseline (in the opinion of the investigator) noted during the ECG evaluations should be recorded on the appropriate AE page of the eCRF. This will assist the sponsor/designee in collecting additional information about that abnormality, including information regarding relationship to study drug or other causes, any action taken, and outcome.

6.1.10 Gastrointestinal-specific Testing

Gastrointestinal testing will be done for all subjects in the active treatment group only during or prior to the screening period, as indicated below. Follow-up testing will be performed as necessary according to the guidelines noted below. See [Table 6-1](#) and [Table 6-2](#) for details and scheduling.

6.1.10.1 Upper Gastrointestinal Series with Contrast

An upper GI with small bowel follow through will be performed following the ingestion of barium contrast material. Results from procedures performed within 6 months prior to Visit 1 will also be acceptable.

6.1.10.2 Abdominal Ultrasound

An abdominal ultrasound will be performed. Results from procedures performed within 6 months prior to Visit 1 will also be acceptable.

6.1.10.3 Fecal Occult Blood Testing

Fecal occult blood testing will be performed at screening, Week 12, and at the end of treatment. Subjects with positive results for fecal occult blood for whom a cause is not readily identified (eg, anal fissure) will undergo a confirmatory colonoscopy/sigmoidoscopy. If no known underlying documented etiology can be attributed to this finding, the results should be discussed with the sponsor's Medical Monitor.

- Subjects with negative endoscopy findings may enroll in the study.
- Subjects with positive endoscopy findings who receive treatment may enroll in the study.

- Subjects with positive endoscopy findings who do not receive treatment will be excluded from the study.
- In those subjects with positive results for fecal occult blood at the end of the study, the investigator will have to determine the cause for the finding and may perform an additional colonoscopy/sigmoidoscopy, if clinically warranted.

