6 STUDY EVALUATIONS AND PROCEDURES

6.1 Evaluations for Safety and Tolerability

Safety variables will be assessed by the following evaluations, according to Schedules of Evaluations and Procedures as outlined in [Table 6-1](#) and [Table 6-2](#). Safety variables for the standard of care group are displayed in [Table 6-3](#) and [Table 6-4](#).

- Adverse events, including GI symptoms. A GI Symptom History Worksheet will be completed daily during the screening period, prior to baseline. GI symptoms will be

recorded as none, mild, moderate, or severe. The principal investigator will assess the aggregate diary entries to determine a baseline of GI symptoms for each subject.

- Physical examinations
- Vital signs, including temperature, heart rate, and blood pressure, body weight, head circumference (up to 36 months of age), height or length, and trends on growth charts
- Electrocardiograms
- Laboratory safety data, including clinical chemistries, hematology, and urinalysis
- Change in urine output (collected or calculated volume)
- Fecal output (by volume or number of bowel movements per day)
- Antibodies to teduglutide (active treatment groups only). Samples for antibody analysis will be drawn at baseline and at the EOT (Week 24 or early termination) visits prior to the administration of teduglutide and at least 14 hours after the previous dose. One additional sample will be collected at the final visit 4 weeks after the EOT (EOS, Week 28). If subjects are determined to have positive/specific antibodies at Week 28 or EOS, they will be asked to return for a follow-up clinic visit 3 months post EOT for another antibody sample. If the subjects continued to have positive/specific antibodies at 3 months post EOT, they will be asked to return for a follow-up visit 6 months post-treatment in order to determine their antibody status.
- GI-specific testing (active treatment groups only) including colonoscopy or sigmoidoscopy, abdominal ultrasound, fecal occult blood testing, UGI/SBFT

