Concomitant medication	X	X	X	X	X	X	X	X	X	X	X	X	X	X

EN = enteral nutrition; EOS = end of study; EOT = end of treatment; ET = early termination; PN/IV = parenteral nutrition/intravenous fluid

^a If fecal/occult blood is positive without explanation, then a colonoscopy/sigmoidoscopy may be warranted

^b Citrulline should be collected 2 to 4 hours postprandially, whenever possible.

^c Intake Diaries will collect data on PN/IV support volume, EN (formula and specialized electrolyte solutions), and regular diet/drink taken DAILY.

^d Urine/Stool Output Diary will collect data on urine and stool output for the 48 hours prior to the next scheduled visit or telephone contact.

^e Nutritional support includes PN/IV, EN feeds (formula and other specialized electrolyte solutions), and regular diet/drink.

^f Nutritional support adjustments can be made after review of the subject's intake and output data recorded on the diaries and the subject's safety lab data following the guidance for nutrition support adjustment provided in [Appendix 1](#).

^g Female subjects of child-bearing potential

^h Head circumference is to be collected as appropriate (ie, up to 36 months of age).

ⁱ At site visits, safety lab assessments consist of serum chemistry, hematology and urinalysis. For safety lab assessment done approximately 7 days following any PN/IV adjustment and/or in between site visits, safety labs consist of serum chemistry and urinalysis. Safety labs performed during site visits must be processed via central lab. Safety labs performed at alternate times in between site visits may be collected by a Home Health Agency and processed for submission to the central lab.

^j Antibody blood draw is to be taken prior to the last dose of study drug, at least 14 hours following the previous dose of study drug. Subjects who test positive/specific for antibodies to teduglutide at the Week 28 visit will have follow-up blood draws for positive/specific antibodies to teduglutide at approximately 3 months following the last dose of study drug. If antibodies are still positive/specific they will be collected again approximately 6 months after the last dose of study drug.

^k If a subject terminates from the study prematurely, all EOT procedures should be done at the time of termination and a follow-up visit should be scheduled 4 weeks later.

^l A visit to the site may be undertaken, if necessary, instead of a phone contact and completed as an Unscheduled Visit.

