Table 6-3 Schedule of Evaluations and Procedures – Screening to Week 12 – Standard of Care Group

Procedures	Screening	Baseline	Week 1	Week 2	Week 3	Week 4	Week 5	Week 6	Week 7	Week 8	Week 9	Week 10	Week 11	Week 12
Visit Number:	1	2	3	4	5	6	7	8	9	10	11	12	13	14
Visit Type	Site	Site	Site	Site	Phone	Site	Phone	Site	Phone	Site	Phone	Site	Phone	Site
Study Day	≥-14	0	7	14	21	28	35	42	49	56	63	70	77	84
Visit Window (days)			± 2	± 2	± 2	± 2	± 2	± 2	± 2	± 2	± 2	± 2	± 2	± 2
Informed Consent ^a	X													
Eligibility	X	X												
Demographics	X													
Medical history	X													
SBS history	X													
Dispense GI Symptoms History Worksheet	X													
Review GI Symptoms History Worksheet		X												
Citrulline ^b		X												X
Dispense Intake and Urine/Stool Output Diaries	X	X	X	X		X		X		X		X		X
Review Intake and Output Diaries ^{c, d}		X	X	X	X	X	X	X	X	X	X	X	X	X
Review nutritional support usage ^e	X	X	X	X	X	X	X	X	X	X	X	X	X	X
Nutritional support adjustment (as needed) ^f			X	X	X	X	X	X	X	X	X	X	X	X
Physical examination and vital signs including weight	X	X	X	X		X		X		X		X		X

Table 6-3 Schedule of Evaluations and Procedures – Screening to Week 12 – Standard of Care Group

Procedures	Screening	Baseline	Week 1	Week 2	Week 3	Week 4	Week 5	Week 6	Week 7	Week 8	Week 9	Week 10	Week 11	Week 12
Visit Number:	1	2	3	4	5	6	7	8	9	10	11	12	13	14
Visit Type	Site	Site	Site	Site	Phone	Site	Phone	Site	Phone	Site	Phone	Site	Phone	Site
Study Day	≥-14	0	7	14	21	28	35	42	49	56	63	70	77	84
Visit Window (days)			± 2	± 2	± 2	± 2	± 2	± 2	± 2	± 2	± 2	± 2	± 2	± 2
Height (length) and head circumference ^g	X	X				X				X				X
Electrocardiogram	X													X
Safety laboratory tests ^h	X	X	X	X	(X)	X	(X)	X	(X)	X	(X)	X	(X)	X
Adverse events	X	X	X	X	X	X	X	X	X	X	X	X	X	X
Concomitant medications	X	X	X	X	X	X	X	X	X	X	X	X	X	X

EN = enteral nutrition; GI = gastrointestinal; PN/IV = parenteral nutrition/intravenous fluid; SBS = Short Bowel Syndrome

^a Informed Consent and, if applicable, informed assent must be obtained prior to performing any study-related procedure.

^b Citrulline should be collected 2 to 4 hours postprandially, whenever possible.

^c Intake Diaries will collect data on PN/IV support volume, EN feeds (formula and specialized electrolyte solutions), and regular diet/drink taken DAILY.

^d Urine/Stool Output Diary will collect data on urine and stool output for the 48 hours prior to the next scheduled visit or telephone contact.

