19.1. ADVERSE EVENTS

Adverse Events (AEs) will be coded using *Medical Dictionary for Regulatory Activities (MedDRA) central coding dictionary, Version 19.1*. Investigator verbatim as well as preferred terms and system organ classes will be included in the listings.

Treatment-emergent adverse events (TEAEs) are defined as AEs that started or worsened on or after the date of first dose for treatment arms and adverse events that started or worsened on or after the baseline visit for standard of care group. For events that start or worsen on the date of

Document:	\\quintiles.net\Enterprise\Apps\sasdata\SASa\sas\Shire\Teduglutide\Biostatistics\Documentation\SAP\TE D-C14-006_SAP_Final_V1.0_20170714		
Author:	PPD	Version Number:	Final V1.0
		Version Date:	14Jul2017
Template No:	CS_TP_BS016 – Revision 3	Reference:	CS_WI_BS005
Effective Date:	01May2012		

first dose, any available start time will be compared to the time of first dose for the treatment arms.

See [Appendix 2](#) for handling of partial dates for AEs. In the case where it is not possible to define an AE as treatment-emergent or not, the AE will be classified by the worst case; i.e. treatment-emergent.

An overall summary of number of subjects within each of the categories described below will be provided as specified in the templates. Adverse events will be summarized using descriptive statistics (e.g., number and percentage of subjects) for each treatment arm and dose group. The number of events will also be presented except for summaries by highest category. The summary will include any TEAE, severity of TEAEs (highest category), investigator assessment of relationship of TEAEs to study drug, treatment-emergent serious AEs (TESAEs), investigator assessment of relationship of TESAEs to study drug, TEAEs leading to discontinuation and TEAEs leading to death.

Listings will include both TEAEs and Non-TEAEs (unless specified otherwise) and will be provided for serious adverse events, adverse events leading to death, and adverse events leading to discontinuation of study drug. Listings will indicate whether an AE is treatment emergent or not.

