19.4. GASTROINTESTINAL-SPECIFIC TESTING

GI-specific testing will be reported for the teduglutide treatment arm only. The clinically significant abnormal results will be presented in a data listing. The results of upper gastrointestinal (GI) series with small bowel follow through, abdominal ultrasound, and colonoscopy or sigmoidoscopy will be reported as 'Normal', 'Abnormal, not clinically significant', or 'Abnormal, clinically significant'. Fecal occult blood testing will be reported as 'Negative', 'Positive, not clinically significant', 'Positive, clinically significant'.

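### On-treatment occult blood testing is scheduled in the teduglutide arms only, so test-detected adverse events are under-ascertained in the standard of care column of the TEAE tables

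*Protocol*

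**What the plan says.** **Testing.** Protocol 6.1.10.3: "Fecal occult blood testing will be performed at screening, Week 12, and at the end of treatment". Protocol 6.1.10: "Gastrointestinal testing will be done for all subjects in the active treatment group only". The safety variable list in Protocol 6.1 repeats the restriction: "GI-specific testing (active treatment groups only) including colonoscopy or sigmoidoscopy, abdominal ultrasound, fecal occult blood testing, UGI/SBFT". Tables 6-1 and 6-2 (active groups) mark the occult blood test at screening, Week 12 and Week 24. Tables 6-3 and 6-4 (standard of care) have no row for it or for endoscopy.

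**Endoscopy.** Protocol 6.1.10.3 says that subjects with an unexplained positive "will undergo a confirmatory colonoscopy/sigmoidoscopy". For positives at the end of the study, the same section leaves a further procedure to the investigator. Table 6-1 marks endoscopy at screening only. Table 6-2 shows it in brackets at Week 24, with the footnote "If fecal/occult blood is positive without explanation, then a colonoscopy/sigmoidoscopy may be warranted".

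**From finding to adverse event.** Protocol 6.1.6 makes a test result an adverse event when it is a clinically significant worsening against baseline or known history. Section 6.1.6.1 lists the occult blood test and endoscopy among the procedures it covers. Protocol 6.1.1.1 also counts certain events caused by procedures that the protocol requires.

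**Tabulation.** SAP 19.1 defines treatment-emergent events for standard of care as well, and states: "Adverse events will be summarized using descriptive statistics (e.g., number and percentage of subjects) for each treatment arm and dose group". SAP Appendix 1 puts Standard of Care in a column after Total Teduglutide. SAP 19.1.1.2 drops standard of care from the by-relationship summaries only. SAP 19.4: "GI-specific testing will be reported for the teduglutide treatment arm only". That sentence covers the test results, not the adverse events that come from them.

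**The concern.** The two sides of the table are not searched with the same effort. Teduglutide children have two scheduled on-treatment chances for occult blood, and then possibly a polyp or a procedural complication, to be found. Standard of care children have none under the protocol. Events found this way go into the same table as events reported spontaneously, and nothing in the table tells the reader which are which.

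This matters because the affected terms will be read closely: colorectal polyps are an identified risk in Protocol 6.1.4. Standard of care is also the only untreated reference in the study. The plan is wholly descriptive, so adjacent percentages are all the evidence it offers on drug versus no drug. A few events against none can be read as a drug effect when some of them reflect the testing schedule.

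**Working it through.** The plan gives no figure on this point. The sample size rests on feasibility (Protocol 8.7), so there is nothing to reproduce. The check has two parts.

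**1. The schedule.**

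- Active children: about 20 (Protocol 4.1), each with two post-baseline tests (Week 12 and Week 24): 20 × 2 = 40 scheduled tests if all complete.
- Standard of care children: up to 8 (Protocol 4.1), each with 0 scheduled tests: 8 × 0 = 0.

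Scheduled tests therefore contribute no events to the standard of care column, whatever the background rate.

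**2. An illustration of size with no drug effect.** Let p be the probability that one on-treatment test yields a new finding recorded as an adverse event. The documents give no value, so p = 1%, 2% and 5% are assumptions. With two independent tests:

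- probability per child: s = 1 − (1 − p)²
- expected children affected: 20 × s
- probability of at least one child among 20: 1 − (1 − s)²⁰

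| Assumed p | s | Expected of 20 | At least one of 20 | Expected of 8 if standard of care were tested alike | Standard of care, scheduled tests |
|---|---|---|---|---|---|
| 1% | 1.99% | 0.4 | 33% | 0.16 | 0 |
| 2% | 3.96% | 0.8 | 55% | 0.32 | 0 |
| 5% | 9.75% | 2.0 | 87% | 0.78 | 0 |

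**Dependence between tests.** If the same children were positive at both tests, the probability per child would fall from s towards p. The expected counts would then fall towards 20 × p = 0.2, 0.4 and 1.0.

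**The screening test.** Every active child is also tested at screening, and only a worsening counts as an adverse event. If background positivity is fully persistent, it already shows at screening and new findings approach zero.

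**Dose contrast.** Both dose groups follow Tables 6-1 and 6-2, so ascertainment by schedule is the same in both.

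**The case against.** The strongest objection is that nothing is inferred from this contrast. Standard of care is a self-selected observational group of up to 8. SAP 7.5 makes no claims of significance, SAP 19 rules out statistical comparisons of safety data, and by-relationship tables already omit standard of care. Much can also be traced by hand: SAP 19.4 lists clinically significant abnormal test results and SAP 14 lists procedures. This stands as a limit on the consequence. It does not remove the problem, because the columns still sit side by side without a warning.

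Several stronger readings are tempting, and the documents do not support them:

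- *The standard of care rate is zero by construction.* This holds only for protocol-scheduled tests. Protocol 1.3 describes these tests as usual in routine care, and adverse events are collected from standard of care children at every contact. Under-ascertained is the accurate word.
- *Endoscopies are done at Weeks 12 and 24.* On-treatment endoscopy depends on an unexplained positive, and Table 6-1 has no endoscopy mark at Week 12.
- *Two, four or seven of 20 teduglutide children would be affected.* Positive rates of 5%, 10% and 20% per test give 9.8%, 19.0% and 36.0% of children with at least one positive. Those rates are assumed, count positives rather than adverse events, treat tests as independent and ignore the screening test.
- *The any-TEAE and gastrointestinal system organ class rates are inflated.* Each child counts once, so this needs children with no other such event. The documents give no means to estimate how many there would be.
- *Only a table without these events should stand beside standard of care.* That would remove drug-caused polyps or bleeding first found by testing and would understate an identified risk. Blinded review would not prevent this, because only the dose is blinded.

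Finally, the SAP follows protocol Amendment 4 and the protocol supplied is Amendment 2. The later schedule and the separate table shells could not be checked. SAP 19.4 still treats this testing as confined to teduglutide.

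**Conclusion.** The concern holds in a limited form. Ascertainment is unequal between teduglutide and standard of care, and the SAP has no rule that shows it. The descriptive contrast for test-detectable terms is partly a testing artefact. The randomized dose comparison is not touched.

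The size cannot be fixed from the documents. The illustrative range of about 0.4 to 2 of 20 children rests on p between 1% and 5%, independent tests, both tests done in every active child, and no drug effect. Persistence from screening would lower it. This justifies a cheap improvement to the display, not a change to the study or to its main safety tables.

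**What to change.** In SAP 19.1:

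1. Keep the full TEAE tables, with the standard of care column, as primary. The reduced display must not replace them.
2. Flag treatment-emergent events first detected through fecal occult blood testing or the endoscopy it triggers, including procedure complications. Apply the flag in any group, so that a standard of care event found by a routine-care test is treated alike.
3. Fix the flagging rule before unblinding. Base it on matching adverse event dates to the gastrointestinal test results (SAP 19.4) and the procedures listing (SAP 14).
4. Add a supplementary display without flagged events, for any TEAE and for the gastrointestinal system organ class by preferred term. Include any other class into which a flagged event codes.
5. Footnote the TEAE tables to say that this testing was scheduled in the teduglutide arms only.

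The cost is SAP wording, one flag and one extra table, with no change to study procedures. The downside is a judgement on how each event was detected. The adverse event fields listed in Protocol 6.1.1.2 do not include mode of detection, so some matches will be uncertain, above all for routine-care tests in standard of care.
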